6.5.6 Survival and Time to Clinical Events

Survival and time to hospitalizations and clinical events will be analyzed in the FAS, mITT, ECM, ERO, EPP, STF, and SRO analysis sets. Survival analyses that include follow-up beyond the placebo-controlled period will be analyzed in the ERO analysis set. The summaries and analyses of time to death or death equivalent are the same as specified in the M-SAP with the addition of baseline age as a covariate in adjusted models, with the addition that the endpoints of time to death independent of occurrence of death equivalents and time to each of the hospitalization and clinical events will be separately analyzed using the same models, and with an additional adjusted analysis that includes baseline serum NfL level as a covariate. Analysis of time to King's stage 4a or 4b will accommodate interval censoring between ALSFRS-R assessments and will be stratified by baseline King's stage.

6.5.7 CAFS

The primary CAFS analysis is as specified in the MPRDR. Additional, unadjusted CAFS analyses are the same as specified in the M-SAP, including specification that pair-wise comparison of change in ALSFRS-R total score for participants who cannot be ranked by time to death or death equivalent is to the maximum follow-up time at which both participants have an observation, and with the following additions:

1. HHD upper and lower extremity percentage and SVC will be analyzed by CAFS by substituting change from baseline for those secondary efficacy endpoints in place of ALSFRS-R total score,
2. An additional set of CAFS analyses will use multiple imputation to extend follow-up of ALSFRS-R total score, HHD upper and lower extremity percentage and SVC for participants who early terminate, withdraw consent, or are lost to follow-up,
3. An additional set of CAFS analyses will use time to death alone independent of any death equivalent,
4. An additional set of CAFS analyses for ALSFRS-R total score, HHD upper and lower extremity percentage, and SVC will adjust rank scores in a linear model with the

following covariates: time from ALS symptom onset, delta-FRS, baseline use of riluzole, and baseline use of edaravone, and

5. An additional set of CAFS analyses for ALSFRS-R total score, HHD upper and lower extremity percentage, and SVC will adjust rank scores in a linear model with the following covariates: time from ALS symptom onset, delta-FRS, baseline use of riluzole, baseline use of edaravone, and baseline serum NfL level.

The multiple imputation model used to extend follow-up of functional scores for participants who early terminate, withdraw consent, or are lost to follow-up will use linear regression with covariates of: time since symptom onset, delta-FRS, baseline riluzole use, baseline edaravone use, and each observed functional score prior to a missing assessment.

Inference from CAFS analyses is supportive of inference from the Bayesian shared-parameter, repeated-measures model for the primary outcome and supportive of inference from the random-slopes model for the secondary outcome of SVC. Primary inference from CAFS analyses will compare survival by time to death or death equivalent, will compare change in function to the last jointly observed time point, and will adjust for the specified covariates.

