For responder analysis, participants experiencing the unfavorable event (e.g., worsening in bulbar subscale score) are considered non-responders. All participants who die, reach a death equivalent, or early terminate due to disease progression will be considered non-responders. Data missing not due to death, death equivalent, or early terminate due to disease progression will be imputed under an assumption that data are conditionally missing at random (MAR). Under MAR, monotone missing data for participants will be imputed using available data from participants within the treatment group to which the participant was randomized. Sensitivity analyses based on multiple imputation under an assumption that data are missing not at random (MNAR) will be performed as described in the M-SAP.

4. Study Endpoints

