6.5.10 Placebo Multiple Imputation

Placebo multiple imputation analyses are the same as specified in the M-SAP with the addition of baseline serum NfL level as a covariate and will be applied to the mixed model repeated-measures analysis of ALSFRS-R total score and the random-slopes analysis of SVC in the FAS analysis set.

The following SAS code specifies the imputation for an endpoint measured every 8 weeks:

```
proc mi data=work.outcomes seed=xxx nimpute=50 out=work.out_mi01
    minimum=. . . . . x x x x maximum=. . . . . y y y y minmaxiter=1000;
    class rlz edv trtrnd;
    fcs reg(Wk08 = sx2b1 dFRS rlz edv Wk00);
    fcs reg(Wk16 = sx2b1 dFRS rlz edv Wk00 Wk08);
    fcs reg(Wk24 = sx2b1 dFRS rlz edv Wk00 Wk08 Wk16);
    mnar model( Wk08 Wk16 Wk24 / modelobs=(trtrnd="0"));
    var sx2b1 dFRS rlz edv Wk00 Wk08 Wk16 Wk24;
run;
```

where Wk00, Wk08, Wk16, and Wk24 are the values of a given efficacy endpoint at the Baseline, Week 8, Week 16, and Week 24 Visits, respectively, trtrnd has a value of zero (0) for participants randomized to placebo, and x and y take appropriate values to specify the range of a given outcome measure (i.e., 0 and 48 for ALSFRS-R total score; 0 and . for HHD upper and lower extremity percentages and SVC).

Inference from these analyses is supportive of inference from the Bayesian shared-parameter, repeated-measures model for the primary endpoint and assess sensitivity to the missing data assumption of the random-slopes linear mixed model for SVC in the FAS analysis set. A separate analysis will include centered baseline serum NfL level as an additional covariate in both imputation stages.

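### The imputation model that extends follow-up for one supportive set of CAFS analyses leaves out treatment group, so any effect accruing after dropout is partly lost

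*SAP*

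**What the plan says.** SAP Section 6.5.7 lists several additions to the CAFS analyses. Item 2 reads in part: "An additional set of CAFS analyses will use multiple imputation to extend follow-up of ALSFRS-R total score". It also covers HHD upper and lower extremity percentage and SVC, and it applies "for participants who early terminate, withdraw consent, or are lost to follow-up". The section then states its own imputation model, a linear regression on "time since symptom onset, delta-FRS, baseline riluzole use, baseline edaravone use, and each observed functional score prior to a missing assessment". Treatment group does not appear, and no sentence says that the regression is fitted by arm or that one arm serves as reference.

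The same section limits the role of these analyses. The main CAFS comparison "will compare change in function to the last jointly observed time point", so it uses no imputed values. More generally, "Inference from CAFS analyses is supportive of inference from the Bayesian shared-parameter, repeated-measures model for the primary outcome".

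Elsewhere the SAP is explicit about the role of treatment arm:
- Section 3.6, for responder endpoints under missing at random (MAR): missing data "will be imputed using available data from participants within the treatment group to which the participant was randomized".
- Section 6.5.10: a placebo-based imputation, with a missing-not-at-random statement that names the placebo arm as the source.
- Sections 6.5.2 and 6.5.3: mixed models with treatment and its interaction with time, which handle missing data under MAR.

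**The concern.** An imputation model should normally contain the variable that the later analysis compares. If it does not, people with the same earlier scores get the same predicted future whichever arm they were in, and any difference that would have built up between them after dropout is not reproduced.

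Item 2 is presented as a way of extending follow-up, not as a stress test, so a reader would take it as a MAR analysis. If it is attenuated, it would show somewhat too little benefit, or too little harm. It could also agree with the main CAFS comparison for the wrong reason: both may be diluted by dropout, and their agreement would look like robustness to dropout.

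**Working it through.** The documents give no bias, power or dropout figure for this imputation, so there is nothing to reproduce. The mechanism was checked by simulation.

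**Inputs from the documents**
- Covariates, as quoted from SAP 6.5.7.
- Visit spacing: every 4 weeks for ALSFRS-R and every 8 weeks for SVC and HHD (SAP 2.9).
- 120 active and 40 placebo within the regimen (protocol summary), plus shared placebo from regimens A, B and C (SAP 6.1). The number shared is not given.

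**Assumptions**
- 160 placebo in total, with 120 vs 40 as a check.
- Placebo slope -1.1 points/month, slope SD 0.7, residual SD 1.2.
- 30% slowing that continues after dropout, or no effect.
- Random dropout of 10%, 20% or 30%, equal in both arms, after at least one post-baseline visit. No deaths.
- 400 trials per scenario and 10 imputations per trial.

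**Formulas**
- Imputation at visit j: score_j = b0 + b1 × delta-FRS + b2 × baseline score + terms for all earlier scores + error, drawn sequentially. The alternative adds b3 × treatment. Time since onset, riluzole and edaravone were not simulated.
- Win difference = mean over all active-placebo pairs of sign(24-week change, active, minus 24-week change, placebo).
- Share retained = win difference after imputation / win difference with full data.

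**Results, 30% slowing, 120 vs 160**

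| Visits | Dropout | Full data | No treatment term (share) | Treatment term (share) | Last shared visit (share) |
|---|---|---|---|---|---|
| 4-weekly | 10% | 0.2345 | 0.2246 (0.958) | 0.2335 (0.996) | 0.2228 (0.950) |
| 4-weekly | 20% | 0.2321 | 0.2140 (0.922) | 0.2311 (0.995) | 0.2115 (0.911) |
| 4-weekly | 30% | 0.2404 | 0.2128 (0.885) | 0.2392 (0.995) | 0.2080 (0.865) |
| 8-weekly | 10% | 0.2326 | 0.2241 (0.963) | 0.2322 (0.998) | 0.2240 (0.963) |
| 8-weekly | 20% | 0.2320 | 0.2155 (0.929) | 0.2313 (0.997) | 0.2148 (0.926) |
| 8-weekly | 30% | 0.2277 | 0.2036 (0.894) | 0.2272 (0.998) | 0.2030 (0.892) |

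The loss without the treatment term runs from 1 - 0.963 = 3.7% to 1 - 0.885 = 11.5%. With the term it is at most 0.5%. For 120 vs 40 at 20% dropout, the shares are 0.2280 / 0.2466 = 0.925 without the term and 0.2447 / 0.2466 = 0.992 with it. The mean difference behaves alike: 1.65 against 1.78 points with full data (4-weekly, 20% dropout).

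**No effect.** The win difference without the term lay between -0.0046 and 0.0055, with standard errors of 0.0031 to 0.0036. That is within simulation error of zero.

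**Effect that stops at dropout.** This was checked on the mean difference with other assumed values (decline 1.0 vs 0.7 points/month, slope SD 0.65, residual SD 1.5, 4-weekly visits). If active participants decline at the placebo rate after leaving, the model as written recovers 101% of the true difference at 15% missing and 102% at 30%. The model with treatment recovers 110% and 123%. A repeat with dropout spread evenly over visits again gave 101% and 102% without the term, and 108% and 117% with it.

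The 8-weekly runs change only the visit spacing. They keep ALSFRS-R-like variability and are not calibrated to SVC or HHD.

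**The case against.** The strongest reply is that the pull towards zero depends on what happens after people leave. Those imputed have left the study, and their later treatment is unknown. If benefit stops when they leave, the arm-free model is the more accurate one. This stands: the bias is conditional. But the SAP's mixed models adopt MAR for such data, and item 2 gives no sign of departing from that.

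The second reply is scope, and it also stands. Only item 2 uses imputed values, all CAFS inference is supportive, and CAFS is not in the testing hierarchy of SAP 6.5.1. The comparison at the last shared visit shrinks by a similar or slightly larger amount, so item 2 is no worse than the main CAFS comparison. The same fact shows that item 2 recovers little of what it was added to recover.

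Some stronger readings are tempting but unsupported:
- That the imputed scores are simply averaged over arms. They are conditional on earlier scores, which carry the effect seen before dropout.
- That the SAP contradicts itself because Section 3.6 imputes within arm. That rule is given for responder analyses, and the same section lets missing-data handling vary with the method of analysis.
- That the placebo imputation in Section 6.5.10 already supplies a conservative CAFS. It is applied to the repeated-measures analysis of ALSFRS-R and the random-slopes analysis of SVC, not to CAFS or HHD.
- That site of onset and Nuedexta use must be added too. No calculation here supports that. The four baseline covariates match those of the adjusted CAFS in item 4.

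The Master SAP was not available. It is unlikely to settle the matter, because Section 6.5.7 states its own covariate list and Section 1 of the SAP ranks the regimen SAP above it.

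**Conclusion.** The omission is plain in the text; its consequence is small and conditional. If a true effect continues after dropout, the item 2 win difference is pulled towards zero by about 4% to 12% at 10% to 30% dropout, against less than 1% with treatment in the model. These figures rest on assumed slopes, variances, dropout and number of shared placebo participants, with deaths left out. Under no effect there is no bias, so false positives are not at issue.

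A reader might infer that the trial's CAFS result, or its main efficacy conclusion, is biased. The documents do not support that, since neither the primary CAFS inference nor the primary Bayesian analysis uses these imputed values. The point is a minor one: as written, item 2 is neither a MAR extension of follow-up nor a declared reference-based analysis, and its result would be hard to interpret.

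**What to change.** In SAP 6.5.7, add treatment group to the covariates of the imputation regression, or fit it separately by randomised group. State that item 2 is a MAR extension of follow-up, in line with the mixed models. If an arm-free, conservative analysis was intended, keep it only as a sensitivity analysis beside the MAR version. Label it as such and give the assumed behaviour after dropout, as Section 6.5.10 does for its placebo-based imputation. The two results would then bracket the two post-dropout assumptions examined here.

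The cost is one model term and a sentence or two of text. No data collection, sample size or primary analysis changes.

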6.5.8 HHD0 and HHD0²

Analyses of HHD0 are the same as specified in the M-SAP with the addition of parallel analyses of HHD0², with a separate analysis that includes baseline serum NfL level as an additional covariate, and with the clarification that time to zero strength for both analyses is interval censored between HHD assessments.

6.5.9 Quantitative Voice Measures

Given the high frequency of voice recordings, a repeated-measures analysis with unstructured covariance is overly flexible but the assumption of linear change required by the random-slopes model may be overly rigid. To complement estimates from the random-slopes linear mixed model, quantitative voice characteristics will be analyzed in a linear mixed model in which the temporal profile for both fixed and random terms is modeled using cubic B-splines with knots at 8 and 16 weeks. The model will include fixed terms for B-splines (4 terms), treatment group (2 levels), treatment group × B-spline interaction, centered time since symptom onset and centered time since symptom onset × B-spline interaction, centered delta-FRS and centered delta-FRS × B-spline interaction, centered baseline riluzole use and centered baseline riluzole use × B-spline interaction, centered baseline edaravone use and centered baseline edaravone use × B-spline interaction, centered baseline Nuedexta use and centered baseline Nuedexta use × B-spline interaction, and centered site of symptom onset (bulbar vs. non-bulbar) and centered site of symptom onset × B-spline interaction. The model will include random regimen-specific intercepts and slopes with unstructured covariance, random participant-specific B-splines (5 terms) with unstructured covariance, and a first-order autoregressive structure for residuals. A simplified covariance structure assuming no regimen-level covariance, heterogeneous compound symmetric covariance among the random B-splines, conditional independence of residuals, or a combination of the three simplifying assumptions will be used if the full model fails to converge. The primary estimand will be the treatment-dependent difference in 24-week change from baseline. The estimate and its 95% Wald confidence bounds will be obtained by a linear contrast of adjusted means. A separate analysis will include centered baseline serum NfL level and the interaction of centered baseline serum NfL level and B-splines as additional covariates.

6.5.10 Placebo Multiple Imputation

Placebo multiple imputation analyses are the same as specified in the M-SAP with the addition of baseline serum NfL level as a covariate and will be applied to the mixed model repeated-measures analysis of ALSFRS-R total score and the random-slopes analysis of SVC in the FAS analysis set.

The following SAS code specifies the imputation for an endpoint measured every 8 weeks:

```
proc mi data=work.outcomes seed=xxx nimpute=50 out=work.out_mi01
    minimum=. . . . . x x x x maximum=. . . . . y y y y minmaxiter=1000;
    class rlz edv trtrnd;
    fcs reg(Wk08 = sx2b1 dFRS rlz edv Wk00);
    fcs reg(Wk16 = sx2b1 dFRS rlz edv Wk00 Wk08);
    fcs reg(Wk24 = sx2b1 dFRS rlz edv Wk00 Wk08 Wk16);
    mnar model( Wk08 Wk16 Wk24 / modelobs=(trtrnd="0"));
    var sx2b1 dFRS rlz edv Wk00 Wk08 Wk16 Wk24;
run;
```

where Wk00, Wk08, Wk16, and Wk24 are the values of a given efficacy endpoint at the Baseline, Week 8, Week 16, and Week 24 Visits, respectively, trtrnd has a value of zero (0) for participants randomized to placebo, and x and y take appropriate values to specify the range of a given outcome measure (i.e., 0 and 48 for ALSFRS-R total score; 0 and . for HHD upper and lower extremity percentages and SVC).

Inference from these analyses is supportive of inference from the Bayesian shared-parameter, repeated-measures model for the primary endpoint and assess sensitivity to the missing data assumption of the random-slopes linear mixed model for SVC in the FAS analysis set. A separate analysis will include centered baseline serum NfL level as an additional covariate in both imputation stages.

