6.5.2 Repeated-measures Model

The specification of the repeated-measures linear mixed model and the primary linear contrast for estimating differences in 24-week change from baseline in a given continuous efficacy endpoint (ALSFRS-R total and domain scores, SVC, HHD upper extremity, lower extremity, and global average percentages, FVC by home spirometry, serum creatinine, serum NfL, ALSAQ-40 domain scores and SI, CNS-BFS total score, and CNS-LS score) are revised from those specified in the M-SAP to include a main effect of treatment and main effects of centered baseline Nuedexta use, centered site of symptom onset (bulbar vs. non-bulbar), and their interactions with visit as additional covariates.

The model will include fixed terms for discrete visit, treatment group, treatment group \times visit interaction, centered time since symptom onset and centered time since symptom onset \times visit interaction, centered delta-FRS and centered delta-FRS \times visit interaction, centered baseline riluzole use and centered baseline riluzole \times visit interaction, centered baseline edaravone use and centered baseline edaravone \times visit interaction, centered baseline Nuedexta use and centered baseline Nuedexta use \times visit interaction, and centered site of symptom onset (bulbar vs. non-bulbar) and centered site of symptom onset \times visit interaction. The following equations describe the model with regimen random effects:

$$Y_{ij} = a_{k(i)} + \gamma_1 t_i + \gamma_{2,j} v_j + \boldsymbol{\gamma}'_3 \mathbf{z}_i + \gamma_{4,j} t_i v_j + \boldsymbol{\gamma}'_{5,j} \mathbf{z}_i v_j + \epsilon_{ij} \quad (\text{eqn. 1})$$

$$a_k \sim N(0, \sigma_r^2), \epsilon_{i \cdot} \sim N(\mathbf{0}, \mathbf{R}), \text{Cov}(b_{k(i)}, \epsilon_{ij}) = 0$$

where Y_{ij} is a given efficacy endpoint measured in participant i at visit j , $a_{k(i)}$ is a random intercept for regimen k to which participant i was assigned, v_j is an indicator variable for visit j , \mathbf{z}_i is the vector of covariates (centered time since onset, centered delta-FRS, centered baseline riluzole use, centered baseline edaravone use, centered baseline Nuedexta use, and centered site

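### The placebo multiple imputation (SAP 6.5.10) omits the Nuedexta and bulbar-onset terms used in the models fitted to its output, and its NfL wording and bound lists do not match its code

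*SAP*

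**What the plan says.** SAP 6.5.10 takes the placebo multiple imputation from the master SAP and applies it in the FAS to two analyses: the repeated-measures model of ALSFRS-R total score and the random-slopes model of SVC. It makes three statements that bear on this point.

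- **Covariates.** Each regression uses time since onset, delta-FRS, riluzole, edaravone and the earlier visit values. The longest is "fcs reg(Wk24 = sx2b1 dFRS rlz edv Wk00 Wk08 Wk16". The variable list is "var sx2b1 dFRS rlz edv Wk00 Wk08 Wk16 Wk24".
- **Bounds.** The code prints "minimum=. . . . . x x x x maximum=. . . . . y y y y minmaxiter=1000", and the text below it explains that "x and y take appropriate values to specify the range of a given outcome measure".
- **NfL.** The opening sentence describes the analysis "with the addition of baseline serum NfL level as a covariate". The closing sentence says "A separate analysis will include centered baseline serum NfL level as an additional covariate in both imputation stages".

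For the models fitted to the imputed data, SAP 6.5.2 says that the regimen SAP revises the master-SAP repeated-measures model to include "main effects of centered baseline Nuedexta use, centered site of symptom onset (bulbar vs. non-bulbar), and their interactions with visit as additional covariates". SAP 6.5.3 makes the same addition to the random-slopes model. The printed SAS code in both sections contains the two terms.

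**The concern.** An imputation model should carry at least the baseline covariates of the model fitted to its output. Here the regimen SAP widened both analysis models and left the imputation regressions without the new terms. Given delta-FRS, time since onset, background treatment and earlier scores, the imputation treats a missing value as unrelated to bulbar onset or Nuedexta use. That assumption is hardest to accept for SVC, where bulbar weakness plausibly affects both the decline and the ability to perform the manoeuvre.

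The analysis is there to show how far the SVC and ALSFRS-R results depend on the missing-at-random assumption. SAP 3.6 also refers to it as the sensitivity analysis for time-to-event endpoints that depend on scheduled assessments. Bulbar status or bulbar score enters four of the five hierarchical secondary endpoints, so a sensitivity analysis that ignores bulbar onset leaves out a covariate of particular interest in this regimen.

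The NfL wording and the bound count are separate and smaller matters. A programmer who follows the opening sentence and one who follows the code would produce different main runs. SAP 7.2 lists selected sensitivity analyses among the supplementary results, which are validated by log inspection only, so the difference might not be noticed.

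**Working it through.** **1. Covariate sets, side by side**

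| Term | Imputation (6.5.10) | Repeated measures (6.5.2) | Random slopes (6.5.3) |
|---|---|---|---|
| Time since onset | yes | yes | yes |
| Delta-FRS | yes | yes | yes |
| Riluzole | yes | yes | yes |
| Edaravone | yes | yes | yes |
| Nuedexta | **no** | yes, by visit | yes, by month |
| Bulbar onset | **no** | yes, by visit | yes, by month |

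**2. Bound count**

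- Minimum list: 5 dots + 4 x = 9. Maximum list: 5 dots + 4 y = 9. Variable list: 4 covariates + 4 visit values = 8. Each list has one entry too many.
- Matched by position, the five dots fall on the four covariates and Wk00. Wk08, Wk16 and Wk24 receive x and y. The fourth x and y have no variable.
- There are four outcome columns and four x/y pairs, so the surplus entry is a dot. Nine entries would fit a list with a fifth baseline covariate. NfL would fit, but the documents do not say that it was NfL.
- Entries needed: 8 as coded; 10 with Nuedexta and bulbar onset; 11 with those two and NfL.

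**3. Possible size of the covariate omission**

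The documents give no slopes, prevalence or dropout by site of onset, so every input here is an assumption: bulbar-onset share q = 0.30; SVC slopes −3.5 and −2.0 percentage points per month; non-bulbar dropout 10%; no treatment effect.

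A rough ceiling comes from supposing that dropouts leave straight after baseline and are imputed at the mean of the placebo completers.

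- Months to Week 24, by the SAP's conversion: 168 × 12 / 365.25 = 5.52.
- Gap at Week 24 between onset groups: G = 1.5 × 5.52 = 8.28 points.
- Bulbar share among placebo completers: s = q(1 − p_P) / [q(1 − p_P) + 0.70 × 0.90], where p_P and p_A are bulbar-onset dropout on placebo and active.
- Bias in the treatment difference: q(p_A − p_P) × G × (1 − s). The error from non-bulbar dropouts is the same in both arms and cancels.

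| Bulbar-onset dropout, active / placebo | s | Bias in treatment difference |
|---|---|---|
| 35% / 35% | 0.236 | 0 |
| 50% / 20% | 0.276 | 0.09 × 8.28 × 0.724 = +0.54 |
| 20% / 50% | 0.192 | −0.09 × 8.28 × 0.808 = −0.60 |

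Simulation lets earlier scores carry part of the information, and so gives smaller values. The runs used these inputs with differing assumed variance components; two of them specified 120 active against 160 placebo participants.

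| Scenario | Result, SVC points at Week 24 |
|---|---|
| Bulbar onset omitted, 35% in both arms | Placebo mean 0.22 to 0.35 too high; treatment difference about zero |
| Bulbar onset omitted, 50% against 20% or the reverse | Treatment difference biased by 0.20 to 0.40 in absolute value, either sign |
| Same, with slope gap cut to 0.5 per month | About +0.14 |
| Same as second row, with delta-FRS in the imputation (assumed correlation 0.6 with slope) | 0.22 to 0.23, against 0.32 to 0.40 in the same run without it |
| Bulbar onset included | All biases within 0.03 of zero |

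On the scale of the SVC analysis, a slope, the run that gave 0.32 to 0.40 points corresponds to 0.06 to 0.07 points per month (0.06 × 5.52 = 0.33; 0.07 × 5.52 = 0.39), or about 0.04 with delta-FRS. The sampling SD of the Week 24 difference in that run was about 1.2 points, so the bias is roughly a quarter to a third of it (0.32/1.2 = 0.27; 0.40/1.2 = 0.33).

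**The case against.** Much of the case on the other side stands.

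- **NfL is largely settled.** The code, the closing sentence and the version 2.0 change entry for 6.5.10 all make NfL a separate run, and other sections (6.5.2 to 6.5.5, 6.5.8 and 6.5.9) do the same. A reader might infer two equally supported plans. The documents do not support that: one clause is out of line with the rest.
- **The surplus bound does little.** By position, Wk08, Wk16 and Wk24 still get their limits. Only Wk00 loses one, and no printed regression imputes Wk00.
- **The imputation conditions on more than earlier scores.** Delta-FRS is a progression-rate covariate and carries part of any bulbar-onset difference in decline.
- **The shorter covariate list may be deliberate.** The CAFS imputation in 6.5.7 uses the same four covariates plus earlier scores, and the master SAP, on which 6.5.10 builds, is not among the documents. Nothing shows an oversight. But no reason is given either, and the regimen SAP takes precedence over the master SAP on these analyses.
- **Other checks may exist.** SAP 6.5.11 brings in the master SAP's sensitivity analyses, so a reader should not infer that this is the only missing-not-at-random check in the trial.

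What remains is that the imputation model is narrower than both analysis models, and that the printed code and text need tidying.

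**Conclusion.** The point holds as a low-cost improvement to a supportive and sensitivity analysis. The mismatch in covariates, the count of nine against eight, and the stray NfL clause are facts of the text. The effect of the mismatch is conditional.

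A reader might infer that imputed values for bulbar-onset dropouts are too optimistic, or that the treatment estimate is biased. The documents support neither as a statement of fact. The first needs bulbar-onset participants to decline faster, beyond what delta-FRS and earlier scores capture, and to drop out more. The second also needs that dropout to differ between arms. With 50% against 20% the bias is about 0.2 to 0.4 SVC points at Week 24, in either direction, and less with delta-FRS in the imputation; with balanced dropout it is about zero. All of these figures rest on assumed slopes, prevalence, dropout and variances.

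The Bayesian primary analysis and the hierarchical tests do not use this imputation and are unaffected.

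**What to change.** In SAP 6.5.10:

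1. Add NDX and bulbar to the VAR statement and to each of the three fcs reg() lines, and to CLASS if they are treated as categorical. If they are left out on purpose, say why.
2. Print one minimum and one maximum per VAR variable: 10 of each in the main run (6 dots and 4 limits), 11 in the separate NfL run (7 dots and 4 limits).
3. Delete "with the addition of baseline serum NfL level as a covariate" from the opening sentence, so that NfL enters only in the separate analysis described at the end of the section.

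The cost is a few words of text and code. Both covariates are already in the analysis models, so no new data are needed, and the power of the primary and hierarchical tests does not change.
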